5.3 Description of Study Process

5.3.1 Instrument Administration / Interviewing Procedures

Manual Refinement:

For the manual refinement phase of the study, bereaved surrogate decision-maker stakeholders will be referred by clinicians and word of mouth. Clinician stakeholders will be referred by study investigators and colleagues based on their expertise. Interviews with stakeholders will be conducted over the phone, through videoconferencing, or in a room at WCM/NYP or MSK that is quiet and private. Stakeholder participants who enroll will be provided with the EMPOWER intervention manual and will be asked to review it. Feedback will be

obtained via interview and will be audio-recorded. Stakeholders may alternately choose to provide their feedback as written comments. After the manual is revised based on stakeholder feedback, stakeholders will be provided with a summary of the changes made and a copy of the revised manual and will be asked if they have any additional comments or suggestions in a survey that also asks for background information. We will additionally make intervention refinements based on our experiences in the open trial. The only measures used in this phase of the study will be the Stakeholder Demographics form and the qualitative interview.

Open Trial and RCT:

Research assistants will screen charts and obtain permission to approach from a member of the patient's care team, such as, but not limited to physicians or nurses. Additionally, in service of determining optimal screening procedures for the purposes of planning a larger trial, clinical staff such as, but not limited to nurses, will be surveyed to identify surrogate decision-makers of patients that they consider to be distressed and would benefit from the EMPOWER intervention. Research staff will approach eligible surrogate decision-makers either in-person or over the phone and explain the study purpose, process, location, time, risks/ benefits, and compensation in detail, assuring them of their privacy and the protocol for addressing acute distress. For potential participants that are unable to be located during normal business hours in the ICU, a note will be left in the patient's room indicating that study staff will contact them via telephone. Staff will confirm comprehension and provide opportunities for questions and concerns. Surrogate decision-makers of adult patients will be screened for the extent to which they are dependent on the patient and anxious, in addition to screening for suicidal ideation, after providing study consent. If they are eligible, then the T1 assessment will take place or be scheduled. For those participants in open trials or randomized to the treatment condition, attempts to schedule an EMPOWER session will be made, with efforts made to accommodate the surrogate decision-makers' schedule.

This procedure is slightly modified for surrogate decision-makers of pediatric patients, who will be screened only for suicidal ideation as exclusion criteria. If eligible, these participants will either complete the PICU-specific brief T1 assessment administered via REDCap, paper, or RA interview, or the brief PICU-specific T1 assessment will be administered by the interventionist at the start of their initial meeting for the EMPOWER intervention or before receipt of EUC resources.

Research staff will assess surrogate decision-makers at T2, T3, and T4 in person, by phone or online. Phone outreach for scheduling assessments or scheduling delivery of either the EMPOWER or EUC interventions, as well as for coordination of other relevant study activities, may occur via texting participants after consent for texting has been obtained. Private/sensitive information outside of coordination of study activities will not be shared via text.

Depending on the status of the patient in the dyad, different measures will be administered as detailed in section 5.2. Expected time burden for the surrogate decision-maker to complete T1, T2, and T3 is approximately 20 minutes. T4, as it consists of a slightly larger battery and an exit interview, takes approximately one hour to complete for those assigned to the EMPOWER intervention. At WCM, \$25 will be deposited on ClinCards, which are debit cards approved by WCM for payment of research participants, after each assessment. Other sites may use their preferred form of payment to compensate the research participants recruited at their respective sites. The research team will aim to administer all assessments in accordance with the time points outlined in this protocol, but due to the context of the ICU caregiving, flexibility will be allowed for participants experiencing major events such as emergent medical situations or bereavement. If patient status is unable to be obtained via the medical record (i.e. due to discharge or transfer to an outside hospital or rehab), participants will be contacted a week prior to the scheduled assessment time point to ensure that the correct questionnaires will be administered. Three attempts, each a week apart, will be made to contact the participant.

Additional data gathered for this study will be obtained from patients' medical charts.

5.3.2 Compensation

Participating stakeholders will receive compensation of a \$50 gift card after reviewing the manual and providing feedback.

Participants in the open trial and RCT will receive compensation of \$100 in ClinCards for completing the 4 assessments (\$25 for each assessment). The ClinCard is a reloadable debit card approved by WCM; other study sites may compensate study participants for the same amount of money with their institution's preferred payment method.

5.4 Adverse Reactions and Their Management

No major adverse reactions are expected.

5.4.1 Reporting Adverse or Unanticipated Events

Potential adverse events (AEs) for this project are expected to be all non-medical in nature.

The Principal Investigators (PIs) will report unanticipated and serious adverse events to the IRB in a timely manner on an ongoing basis. For the purpose of this study, a Serious Adverse Event (SAE) is defined as an event that, as a direct result of the study, causes serious harm to the subject (e.g., that involvement in the study caused the death or serious injury to the subject). AEs are also reported as part of the progress reports in the non-competitive and competitive renewals for the NIH.

Monitoring Safety of Participants:

There are several ongoing mechanisms for monitoring the occurrence of AEs. The study staff will monitor day-to-day study activities. This monitoring is facilitated by: (1) the PIs' telephone numbers provided to participants upon entry into the study to report concerns related to study participation; (2) weekly meetings with project staff and investigators to discuss study progress, reactions to the conduct of the study, and any AEs; and (3) direct supervision of the study interviewers. To address participants' potential psychological distress, the PIs will have a referral list of phone numbers for local mental health service clinicians.

Plans for Assurance Compliance Regarding AE Reporting:

The PIs are required to report AEs to the IRB on an ongoing basis. In addition, yearly IRB renewal submissions require detailed AE reporting. AEs are also reported as part of the progress reports in the non-competitive and competitive renewals for the NIH.

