Efforts targeting the plight of critically ill patients and their informal caregivers have produced mixed results for improving EoL care and informal caregiver mental health. ¹⁰⁻¹² In a recent study of a palliative-care intervention in the ICU designed to reduce caregiver anxiety and depression, PTSD symptoms actually *increased* for those caregivers who received the intervention. ¹² *A primary limitation of these interventions is that they have targeted mental health outcomes but were not explicit mental health interventions.*

We propose here a proof-of-concept study to address this limitation. In response to requests by the directors of the NYPH Medical ICU (MICU), [name] and [name], to address the emotional distress of surrogate decision-makers, we have developed a mental health intervention for surrogate decision-makers of patients in the ICU. We aim to develop further and pilot test this brief mental health intervention called "Enhancing & Mobilizing the POtential for Wellness & Emotional Resilience among Surrogate Decision-Makers of ICU Patients" (EMPOWER) that can be delivered by a trained mental health provider to patient surrogate decision-makers in the ICU. EMPOWER is a cognitive-behavioral, acceptance-based intervention designed to reduce "experiential avoidance"^{3,13} of unpleasant thoughts and feelings related to thinking about the patient's death. EMPOWER targets symptoms of peritraumatic stress and anticipatory grief to reduce experiential avoidance that interferes with optimal decision-making on the patient's behalf. It consists of discrete ~15minute modules that can be delivered flexibly in a setting with multiple interruptions and unexpected crises. The intervention can be delivered in-person or via telehealth. By reducing surrogate decision-makers' experiential avoidance, EMPOWER removes a barrier to ACP, including the completion of advance directives, such as Do Not Resuscitate (DNR) orders. It also is expected to promote the receipt of EoL care consistent with patient values. In this way, EMPOWER should improve EoL care that enhances patient quality of life while also empowering surrogate decision-makers to cope with a loved one's impending death and adjust following the patient's ICU death or discharge. Specifically, we aim to:

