6.1 Data Analysis Plan

Below are descriptions of the statistical procedures performed to test each of the hypotheses. Participant data will be stored in a locked file cabinet and using a secured REDCap database. Missing data will be estimated using a multiple imputation procedure described by Schafer and Olsen³⁷. There will not be a data monitoring committee due to the trial's relatively short duration and the minimal risks the intervention poses. Trial data will

not be independently audited. An interim analysis of the pilot data will occur to inform the conduct of the randomized control and edits to the EMPOWER manual. Data for participants who come bereaved before the administration of EMPOWER or EUC interventions will be treated as exploratory and analyzed separately.

Specific Aim #1: Develop EMPOWER for surrogate decision-makers of critically ill patients who at risk of becoming unable to communicate and/or are currently are unable to communicate in the ICU.

There are no hypotheses for this aim. We will use thematic content analysis, a well-established, systematic qualitative analysis approach in health research, to identify themes from stakeholder participants' narratives and exit interviews. We will follow Morse's²¹ guidelines for conducting rigorous qualitative research (e.g., audit trail, saturation) using Atlas.ti software. We will independently review each interview transcript as well as qualitative data gathered from manual edits and Delphi survey responses and will synthesize and interpret participants' feedback about the content of the EMPOWER manual.

Specific Aim #2: Determine the feasibility, tolerability, acceptability, and preliminary effects of EMPOWER on surrogate decision-maker mental health.

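### The SAE definition makes causation by the study an entry condition, so serious-event counts in surrogates cannot be fairly compared between EMPOWER and enhanced usual care

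*Combined protocol and SAP*

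**What the plan says.** Section 5.4.1 (Reporting Adverse or Unanticipated Events) gives the only SAE definition in the documents. The event must be one that, "as a direct result of the study, causes serious harm to the subject", and the example repeats the condition: "that involvement in the study caused the death or serious injury to the subject".

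On reporting, "The Principal Investigators (PIs) will report unanticipated and serious adverse events to the IRB". The section does not say who judges causality, or whether that person knows the assignment. Ordinary adverse events carry no causality condition ("The PIs are required to report AEs to the IRB on an ongoing basis"), but the term is not defined. They come to light through telephone numbers given to participants "to report concerns related to study participation", weekly staff meetings and supervision of interviewers. Section 5.4.1 describes no scheduled event question.

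On oversight, section 6.1 (Data Analysis Plan) states: "There will not be a data monitoring committee". It also rules out an independent audit. Neither that section nor the analyses for Aims 2 and 3 plan a table of adverse or serious events by arm.

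**The concern.** Seriousness describes what happened to the participant; relatedness is an opinion about why. The usual practice is to record them separately, so that a control arm can show whether serious events are more frequent under the intervention without anyone having to attribute each one. Here the opinion comes first and decides whether the event is recorded as serious at all.

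The opinion is also unlikely to be applied evenly. EMPOWER consists of six one-on-one modules and two booster sessions on distressing material. Enhanced usual care is regular ICU care plus a resource list and an information packet (section 5.2, Study Design). An event after a packet can rarely be called a direct result of the study. The filter could hide a real excess, if events are routinely put down to the patient's illness. It could also create a false one, if only EMPOWER events are ever attributed.

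The plan is meant to inform an application for a larger efficacy trial (section 1.1, Introduction), and that trial would need a serious-event record not already filtered by attribution.

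**Working it through.** There is no stated figure to reproduce: the documents give no expected SAE rate and no attribution rate. The check is of the text, followed by an illustration on assumed rates.

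**Text, step by step**

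1. Causation is required both in the definition and in its example (5.4.1). No cause-free definition of seriousness appears elsewhere.
2. An event judged unrelated can at most enter as an ordinary adverse event. That term is undefined, and no seriousness field is described, so its seriousness is not carried forward.
3. No separate or blinded assessor, monitoring committee, audit or by-arm event table offsets this (5.4.1; 6.1 Data Analysis Plan).
4. Tolerability has a similar filter: drop-out counts only when the participant says the study was too distressing. The T4 exit interview is held only with EMPOWER recipients.
5. Symptoms are treated differently. PDI is compared at T2, and PG-12/13, BEAQ, IES-R, STAI, PHQ-9 and Decision Regret at T3 and T4, with a reduced set for pediatric surrogates. No causality judgement enters.

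**Illustration**

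Inputs from the plan: 40 EMPOWER and 20 enhanced usual care projected (6.1, Statistical power and sample size considerations). Assumed: the same true serious-event rate *p* in both groups; a share *a* of EMPOWER events and *b* of control events judged a direct result of the study.

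True expected count = n × p. Counted SAEs = n × p × a (EMPOWER) or n × p × b (control).

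| p | True, EMPOWER v control | Counted, a = 20%, b = 0 | Counted, a = 50%, b = 0 | Counted, a = 50%, b = 10% |
|---|---|---|---|---|
| 5% | 2 v 1 | 0.4 v 0 | 1.0 v 0 | 1.0 v 0.1 |
| 10% | 4 v 2 | 0.8 v 0 | 2.0 v 0 | 2.0 v 0.2 |
| 20% | 8 v 4 | 1.6 v 0 | 4.0 v 0 | 4.0 v 0.4 |

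The counted rate ratio is the true ratio multiplied by a/b. With a = 50% and b = 10% it is 1 × 0.50/0.10 = 5, although the true ratio is 1. In the other direction, if 3 of 40 and 1 of 20 had a serious psychiatric event and all were attributed to the patient's illness, the record would show 0 against 0.

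**What complete counts could show**

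With four events among 60 people, a 3 v 1 split has probability C(40,3) × C(20,1) / C(60,4) = 9,880 × 20 / 487,635 = 0.41 under no effect. Even for true rates of 10% against 30% the normal-approximation power is about 0.39. The gain from the change is therefore an undistorted descriptive record, not a useful test.

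**The case against.** A reader might infer that harm cannot be compared between the arms at all. The documents do not support that. The most plausible harm, worsening distress, PTSD symptoms, anxiety, depression or grief, is measured on the same schedule in both arms and compared whatever its cause. The introduction's precedent, that "PTSD symptoms actually *increased* for those caregivers who received the intervention", is also no argument for SAE counts: a rise in average symptoms would not be an SAE under any outcome-based definition, and the IES-R is the measure that would detect it. What stands is that scale means do not count deaths, suicide attempts or admissions, and that surrogates with such events may be the ones who miss T2 to T4, where missing values are to be imputed.

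It can be said that nothing is lost, since adverse events of any cause go to the IRB and section 5.4.3 (Reaction Management) sends acute self-harm risk to the principal investigators at once. That is true, and an unrelated event is not barred from the record. But the first route rests on an undefined term without a seriousness field, and the second is a management route, not a tabulation.

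A reader might also take it as documented that causality is judged by people who know the assignment. It is not. It is a strong inference, because the arms are visibly different, the investigators meet project staff weekly and the COVID-19 phase is open.

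Finally, a cause-free definition for every subject would misfire. ICU patients are enrolled too (1.1 Overview; 4.0 Informed Consent Process), so expected deaths and hospital stays would become SAEs. Nor would a new definition alone make counts comparable: EMPOWER participants have more staff contact, and the projected 40 include unrandomised participants. These objections stand, and they shape the fix.

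**Conclusion.** The point holds for serious events in surrogate decision-makers. As defined, the SAE count depends on an attribution that is likely to differ by arm and for which no blinded or independent assessor is described, so it cannot be fairly compared between EMPOWER and enhanced usual care. The comparison of average symptoms is unaffected, and so are the planned effect analyses.

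The size cannot be derived from the documents. On the assumed rates, equal true risk gives 0.4 to 4.0 counted SAEs against 0 when no control event is attributed. This rests on lower attribution in the control arm, which is inferred from what that arm receives. The numbers are small and a by-arm table would be descriptive only. The change is still worth making before more participants are enrolled, because it is cheap and seriousness that was never recorded is hard to recover later.

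**What to change.** In section 5.4.1, for surrogate decision-makers and not for the ICU patients:

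- Define an SAE by its outcome regardless of cause, for example death, a life-threatening event, hospitalisation, a suicide attempt or serious injury.
- Record relatedness to the study in a separate REDCap field.
- Ask the same brief event question in both arms at the existing T2, T3 and T4 assessments, for surrogates of adult and pediatric patients alike.

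In section 6.1 (Data Analysis Plan), add a table of all SAEs by arm, with relatedness as a second layer, and show the unrandomised open-trial participants separately. If allocation in the randomised part is 1:1, as the 30:30 plan suggests, 20 controls would be matched by about 20 randomised EMPOWER participants, leaving about 40 − 20 = 20 of the projected 40 unrandomised.

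Expedited reporting to the IRB can stay limited to related or unanticipated events. The cost is a protocol amendment, one short added question at three existing contacts, one database field and slightly more events to log. Surrogates who miss an assessment will still be under-recorded, so the table should state how many answered the question in each group.

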Surrogate decision-makers will be assessed pre-intervention/baseline (Time point 1, T1), post-intervention (within a week of the surrogate decision-maker's completion of the baseline assessment) (Time point 2, T2), 1-months after post-intervention assessment (Time point 3, T3), and 3-months after post-intervention assessment with an additional exit interview with the research staff that will take about 40 minutes to complete for those receiving EMPOWER only (Time point 4, T4). Assessments will be completed using paper-and-pencil assessments, over the phone with research staff, or online (REDCap). The exit interview will be audio recorded and can be in person, over the phone, or over videoconference.

The EMPOWER arm includes 6 modules that are approximately 15-20 minutes each, all delivered by the same interventionist one-on-one in person or if needed, over the phone or video conference. The intervention can be completed in approximately 1.5 to 2 hours in a single sitting in the ICU, or modules can be completed in piecemeal if the surrogate decision-maker prefers or needs to stop because of, for example, the need to attend to the patient or speak with the medical team. If the intervention is completed in piecemeal, it is expected the intervention will occur over the course of 2-3 days, although scheduling will be flexible to not burden participants and be sensitive to needs such as bereavement and urgent medical situations. There are 2 booster sessions (approximately 1 hour each) that are conducted via telehealth medium such as phone or video call 2 and 4 weeks after the initial 6 modules are completed. If the patient dies before the 6 modules are completed, the interventionist will make a condolence call during which he/she will offer to continue the modules if the surrogate decision-maker is interested (during that call or at a separate time). If the surrogate decision-maker declines completion of the 6 modules, the interventionist will indicate that he/she will call again in 2 weeks to offer support and review what they have previously discussed. Due to the wide variety of

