We will compute descriptive statistics to characterize the feasibility and acceptability of EMPOWER by examining helpfulness/satisfaction ratings, rates of recruitment, reasons for refusal, and number of modules/booster calls completed. Targets will include completion of 4/6 modules for feasibility and tolerability. Target acceptability will be an average score greater than 3 on the acceptability items in the post-intervention satisfaction questionnaire among participants who received EMPOWER. Tolerability will also be measured by open ended-responses to qualitative questions asked at T4 regarding negative experiences, emotional difficulties, and perceived costs and benefits of participating in the intervention. Drop-out will not be considered as a metric of tolerability due to the highly stressful and variable circumstances of ICU caregiving, unless participants drop out of the study and specifically express that they consider it to be too distressing. Qualitative data analysis will be used to analyze data from open-ended questions to identify the most helpful components of EMPOWER.

To evaluate the preliminary effects of EMPOWER among participants in the combined RCT and COVID-19 open trial phases, we will use a hierarchical linear modeling (HLM) and an intent-to-treat approach. HLM is statistically appropriate because of the clustering within interventionists and within surrogate decision-makers. HLM will correct for this clustering by modeling interventionists and surrogate decision-makers as random effects, as has been done in prior trials ^{38 39}. This will also provide a treatment assignment model coefficient and effect size estimate for our future, larger study.

HLM modeling will determine differences between surrogate decision-makers and patients assigned to EMPOWER vs. enhanced usual care. The primary outcome is post-intervention (T2) differences in PDI scores. Secondary outcomes are differences in scores on the PGD 12/13 and BEAQ at one-month (T3) and three-month (T4) follow up from T2. Exploratory outcomes are differences in scores on the IES-R, STAI, PHQ-9 and Decision Regret Scale at one-month (T3) and three-month (T4) follow up. HLM models will include covariates, either as fixed-effect or time-varying, if those variables are found to be significantly statistically associated with both intervention assignment and the outcome examined.

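### Adverse events are captured passively and EMPOWER has more live contact than EUC, so recorded event counts would not be comparable between arms

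*Combined protocol and SAP*

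**What the plan says.** Section 5.4.1 (Reporting Adverse or Unanticipated Events) says staff monitor daily study activities, helped by three things:

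- "telephone numbers provided to participants upon entry into the study to report concerns related to study participation"
- "weekly meetings with project staff and investigators to discuss study progress, reactions to the conduct of the study, and any AEs"
- "direct supervision of the study interviewers"

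The batteries under Measures Used give instruments by title and short description. None is described as an adverse-event question, for adult or paediatric surrogates. The Columbia suicide items are listed for the screener only.

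Contact differs by arm. Under Study Design, "The EMPOWER arm includes 6 modules that are approximately 15-20 minutes each", and these may be given "in a single sitting in the ICU, or modules can be completed in piecemeal". Also: "There are 2 booster sessions (approximately 1 hour each", held by phone or video 2 and 4 weeks after the modules. The T4 exit interview is for EMPOWER recipients only. EUC is a resource list and information packet that may be mailed or sent as a pdf. Assessments in either arm may be on paper, by phone or online.

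The Data Analysis Plan, Aim #2, adds: "Tolerability will also be measured by open ended-responses to qualitative questions asked at T4 regarding negative experiences". It also states that there is no monitoring committee and no independent audit.

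**The concern.** Of the three aids in 5.4.1, only the telephone line comes from participants, and it depends on someone choosing to call. The other two pass on or oversee what staff have already heard. What staff hear depends on how often they speak with a participant, and that differs by arm by design. With equal true risk, more events would be recorded under EMPOWER.

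This matters for safety reporting. The Introduction cites an ICU palliative-care intervention after which caregivers' PTSD symptoms rose, so harm is a live question for this class of intervention. Adverse events go to the IRB and into NIH progress reports, and the pilot is meant to support an application for a larger trial. Without a committee or audit, there is no independent check on the event record. Counts tabulated by arm could make EMPOWER look worse than it is and EUC look quieter than it is.

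**Working it through.** The plan gives no adverse-event rate or count, so there is no figure to reproduce. The check is a count of contacts, followed by an illustration.

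**1. Scheduled contacts after baseline**

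| Contact | EUC | EMPOWER |
|---|---|---|
| T2, T3, T4 assessments | 3 | 3 |
| Module sittings | 0 | at least 1 |
| Boosters | 0 | 2 |
| Total | 3 | at least 6 |

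The exit interview is part of T4, so it is not counted again. It still makes T4 different in kind: it is the only qualitative instrument listed at T4, so the questions on negative experiences would be asked there, of EMPOWER participants alone. The totals assume that modules and boosters are delivered as planned.

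**2. Instruments that might serve as an adverse-event question**

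- The T2 satisfaction questionnaire goes to both arms and covers tolerance. Its items are not shown.
- The EUC tracker at T2 (EUC only) measures use of the resources supplied.
- The adult Medical Information Update at T3 and T4 is not described.
- The check of completed forms under Data Collection looks for missing answers.

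So the supportable statement is that no adverse-event question is listed.

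**3. Illustration**

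Let q be the chance that one contact brings an existing event to light. This is an assumption, taken as equal in both arms and for every contact. With k contacts, detection = 1 − (1 − q)^k.

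| q | EUC, k = 3 | EMPOWER, k = 6 | Ratio |
|---|---|---|---|
| 0.05 | 1 − 0.95³ = 0.143 | 1 − 0.95⁶ = 0.265 | 1.86 |
| 0.10 | 1 − 0.90³ = 0.271 | 1 − 0.90⁶ = 0.469 | 1.73 |
| 0.20 | 1 − 0.80³ = 0.488 | 1 − 0.80⁶ = 0.738 | 1.51 |

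**4. Sensitivity to timing**

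The formula lets every contact find every event, which holds only for events present from the start.

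- Event after T2 and before the first booster: T3 and T4 remain in EUC (k = 2); both boosters, T3 and T4 remain in EMPOWER (k = 4). At q = 0.05: (1 − 0.95⁴)/(1 − 0.95²) = 0.1855/0.0975 = 1.90. At q = 0.20: 0.5904/0.36 = 1.64.
- Event after T3: only T4 remains in each arm, so the ratio is 1.0 on this count. What is left is the difference the exit interview makes.

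A single q also treats an online form and a one-hour session as equally likely to reveal an event. The argument itself implies that they are not, and this simplification probably understates the gap.

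**The case against.** The strongest reply is that both arms are observed on a common schedule for the harm that matters most. The plan expects adverse events to be non-medical, and distress is the reaction it anticipates. PDI, IES-R and STAI are repeated at T1 to T4 in both arms and in both the adult and paediatric batteries. Adults also complete the PHQ-9 at T1, T3 and T4. The T2 questionnaire covers tolerance in both arms. Under Reaction Management, acute risk noticed in a research assessment goes to the investigators whatever the arm.

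This stands against the stronger readings. A reader might infer that adverse events are found only through volunteered calls, or that harm in EUC would go unseen. The documents do not support either: section 5.4.1 presents its three items as aids to daily monitoring, and average worsening in EUC would appear in the scales. The reply does not remove the point, because the plan does not say that scores are reviewed or logged as adverse events, and the scales would not identify an emergency or mental-health visit.

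Second, no between-arm analysis of adverse events is planned, and Aim #2's completion and acceptability targets concern EMPOWER alone. That also stands, so calling the safety data uninterpretable would go too far. A contrast at the projected 40:20 would be imprecise in any case: no events among 20 people is compatible with a true rate of up to 1 − 0.05^(1/20) = 13.9% (one-sided 95% limit).

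Third, closer observation where sessions may provoke distress is defensible. It is, but it calls for separating session-found events from those found by a common method.

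**Conclusion.** The point holds as a matter of comparability. If the plan is followed as written, the chance that an event enters the record depends on arm, and the likely direction is under-recording in EUC. This rests on the contact schedule and on the absence of a listed adverse-event question.

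The size cannot be derived from the documents. On the minimum count of 6 versus 3 contacts, with an assumed 5-20% detection chance per contact, the spurious ratio is about 1.9 to 1.5. It shrinks to 1.0 on the same count for events after T3. A reader might reach larger ratios by counting the exit interview as a further contact, but it belongs to T4, which is already counted.

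The primary PDI comparison at T2 is untouched. The consequence is for safety reporting and for planning the larger trial, which makes this a cheap improvement and not a flaw in the main analysis.

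**What to change.** - Add the same short question to the T2, T3 and T4 forms, in both arms and in the adult and paediatric batteries. It should ask about new or worsened problems and any emergency or mental-health visit since the last assessment.
- Record for each event how it was found: common question, telephone call, module session, booster or exit interview.
- Base any by-arm summary of adverse events on answers to the common question. List events first raised in sessions, boosters or the exit interview separately.

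The cost is one or two REDCap items and a small amendment, about a minute per assessment, and some more reports for staff to review.
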